### 1.3 SCHEDULE OF ASSESSMENTS

**Table 1 Schedule of Assessments**

Week	Screening	Baseline	Treatment Period										EOS				
	-4 to -1		1					2	3	4	8	15	29	43	57	71	
Day	-28 to -3	-2 a			1		2	3	4	8	15	29	43	57	71		
Window	-	-	-	-	-	-	-	-	-	-	±24 hrs	±24 hrs	±24 hrs	±24 hrs	±3 days		
PK Hour (from start of infusion)			0	1	2(T)	3	8	14	24	50	74	170	338	674	1010	1346	1682
Informed consent	X																
Inclusion/exclusion	X	X															
Demographics	X																
Medical history	X	X														X	
Physical examination b	X	X	X									X	X	X	X	X	
Height	X																
Weight	X	X															
Serum pregnancy test c	X	X												X		X	
Urinalysis	X	X										X	X	X	X	X	
HIV, HBsAg, HCV, COVID-19 d , TB	X	COVID-19 Only															
Urine drug abuse screen e	X	X															
Participant confinement f							X										
Vital signs g,h	X	X	X	X	X	X	X	X	X	X	X	X	X	X	X	X	
ECG g,k	X	X	X	X	X	X	X	X	X	X	X	X	X	X	X	X	
Telemetry k							X										
Biochemistry g,l	X	X	X						X	X	X	X	X	X	X	X	
Hematology g	X	X	X						X	X	X	X	X	X	X	X	
PK g,i,l			X	X	X	X	X	X	X	X	X	X	X	X	X	X	
Biomarkers g,j		X				X		X	X	X	X	X	X	X	X	X	
ADA/nAb m		X									X	X	X	X	X	X	
Infusion of study drug			X														
Concomitant medications	X						X					X	X	X	X	X	
Adverse events	X		←													→	

Abbreviations: ACE = angiotensin converting enzyme; ADA = anti-drug antibody; ECG = electrocardiogram; EOS = end of study; FU = follow-up; HBsAg = hepatitis B antigen; HCV = hepatitis C virus; HIV = human immunodeficiency virus; IL-6 = interleukin 6; nAb = neutralizing antibodies; PK = pharmacokinetics; sIL-2R = soluble IL-2 receptor; sTNF $\alpha$  = soluble tumor necrosis factor alpha; TB = tuberculosis.

[figure not shown]
- a Assessments at Day -2 may be performed on Day -1, as needed, by the clinical research unit, but must be performed no later than Day -1.
- b A full physical examination will be performed at Screening, Baseline, Day 8, and Day 71. An abbreviated physical examination will be performed predose on Day 1, and Days 15, 29, and 43. See Section [8.2.1](#) for a description of the physical examination.
- c For women of childbearing potential only. At Baseline, an FSH test will be run to confirm a postmenopausal state in women under 60 years old and not using hormonal contraception or hormone replacement therapy.

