- d At each visit, participants will have a temperature check and will be asked if they have had exposure to someone known to have COVID-19. If the temperature is above 100°F (37.7°C) or the answer is "yes," participants will be tested for COVID-19. Participants who receive a COVID-19 vaccine prior to study entry must receive the final vaccine at least 30 days before dosing and will be tested for COVID-19 as per the SoA. Participants who wish to receive the COVID-19 vaccine after dosing must wait until after Week 4 PK sampling and other assessments have been completed. COVID-19 vaccination and any adverse reaction to the vaccine must be reported.
- e This will include a blood draw to test for blood alcohol levels.
- f From check-in at Day -2 to discharge from the unit on Day 8. Since the participants will be immunocompromised by administration of study treatment, the participants should be instructed to quarantine at home for 6 days after discharge from the clinical research unit.
- g When a meal, vital signs, ECG, or blood sample collection are scheduled at the same time as the study drug administration, the following order will be respected: ECG, vital signs, clinical biomarkers, PK, ADA, safety laboratory samples, and meal. To respect exact timing of PK samples (see [Table 8](#)), the other measurements will be done ahead of the scheduled time. The assessment schedule should be adapted to the design of the study.
- h During infusion, blood pressure and heart rate should be collected every 15 minutes for the first hour, every 30 minutes for the second hour, and hourly for 2 hours after the completion of infusion.
- i Blood samples will be collected for XTMAB-16 PK analysis at predose (Hour 0), at 1 hour after the start of infusion, 1 hour after the start of infusion, immediately after the 2-hour infusion (T; infusion termination), and at 3, 8, 14 hours on Day 1, and at 24 hours (Day 2), 50 hours (Day 3), 74 hours (Day 4), 170 hours (Week 2, Day 8), 338 hours (Week 3, Day 15), 674 (Week 4, Day 29), 1010 (Week 6, Day 43), 1346 hours (Week 8, Day 57), and 1682 hours (Week 10, Day 71) postinfusion of XTMAB-16 or placebo. All sampling time points after time T refer to time from the start of infusion. Acceptable windows for PK sample collection are provided in [Table 8](#). The exact time of sample collection must be recorded on the eCRF.
- j Blood samples will be collected to evaluate biomarker concentrations of ACE, sIL-2R, IL-6, and sTNF $\alpha$ .

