#### 4.1.2 STOPPING RULES

##### 4.1.2.1 CRITERIA

Participants who experience injection site reactions or vital signs changes of Grade 1 or 2 (see [Appendix 4](#)) during infusion may continue infusion or have infusion interrupted for treatment and then resumed, at the discretion of the Investigator. Participants who experience injection site reactions or vital signs changes of Grade 3 or 4 during infusion should have infusion terminated and will be treated, as needed, for the adverse events. Any participant who experiences anaphylaxis during infusion will have infusion terminated; diagnosis of and recommended treatment for anaphylaxis is provided in [Appendix 5](#).

In addition to the assessment of SAEs and the occurrence/severity of other AEs by the Sponsor and the Investigator, after exploring potential confounding factors, the following criteria should be considered as guidance for the decision to stop dose escalation or to stop administration of the study drug to additional participants:

- 1 SAE for which the relationship to treatment cannot be reasonably excluded
- 1 AE of severe intensity for which the relationship to treatment cannot be reasonably excluded
- 3 or more participants with AEs of moderate intensity for which the relationship to treatment cannot be reasonably excluded
- 1 participant in a cohort with potential Hy's Law values
  - ALT or AST  $>8 \times$  upper limit of normal (ULN)
  - ALT or AST  $>5 \times$  ULN for more than 2 weeks
  - ALT or AST  $>3 \times$  ULN and (total bilirubin  $>2 \times$  ULN or INR  $>1.5$ )
  - ALT or AST  $>3 \times$  ULN with the appearance of fatigue, nausea, vomiting, right upper quadrant pain or tenderness, fever, rash, and/or eosinophilia ( $>5\%$ )
- QTcF  $\geq 500$  ms (men and women)
- Any other clinically significant intolerance findings

If any of the above occur, the Contract Research Organization (CRO) and Sponsor should be notified within 24 hours of becoming aware of the event. Decisions to stop dose escalation or stop administration of study drug to additional participants will be determined collectively between the PI, CRO Medical Monitor, and Sponsor.

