#### 8.2.3 VITAL SIGNS

Oral, tympanic or temporal body temperature, respiratory rate, pulse, and systolic and diastolic blood pressure will be assessed. The method of body temperature assessment chosen should be recorded and consistent throughout the study.

If oral temperatures (°C) are taken, participants will have had no food or liquid for at least 5 minutes before assessment.

During the infusion, systolic/diastolic blood pressure and pulse should be measured in a semi-spine/semi-reclined position. For all other readings, blood pressure and pulse will be taken in a supine position after 10 to 15 minutes rest.

Respiratory rate (breaths/min) will be taken after at least 5 minutes rest; breaths are counted for 30 seconds and multiplied by 2. Respiration rate will be taken concurrently with all ECGs. During the infusion, respiration rate will be taken in a semi-supine/semi-reclined position.

---

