**Table 10      Grading for Vital Signs**

Vital Signs *	Mild (Grade 1)	Moderate(Grade 2)	Severe (Grade 3)	Potentially Life Threatening (Grade 4)
Fever (°C) ** (°F) **	38.0 – 38.4 100.4 – 101.1	38.5 – 38.9 101.2 – 102.0	39.0 – 40 102.1 – 104	> 40 > 104
Tachycardia - beats per minute	101 – 115	116 – 130	> 130	ER visit or hospitalization for arrhythmia
Bradycardia - beats per minute***	50 – 54	45 – 49	< 45	ER visit or hospitalization for arrhythmia
Hypertension (systolic) - mm Hg	141 – 150	151 – 155	> 155	ER visit or hospitalization for malignant hypertension
Hypertension (diastolic) - mm Hg	91 – 95	96 – 100	> 100	ER visit or hospitalization for malignant hypertension
Hypotension (systolic) – mm Hg	85 – 89	80 – 84	< 80	ER visit or hospitalization for hypotensive shock
Respiratory Rate – breaths per minute	17 – 20	21 – 25	> 25	Intubation

\* Subject should be at rest for all vital sign measurements.

\*\* Oral temperature; no recent hot or cold beverages or smoking.

\*\*\* When resting heart rate is between 60 – 100 beats per minute. Use clinical judgement when characterizing bradycardia among some healthy subject populations, for example, conditioned athletes.

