4.11.4 Vital Signs, Physical Findings and Other Observations Related to Safety

Vital Signs

Oral, tympanic or temporal body temperature, respiratory rate, pulse, and systolic and diastolic blood pressure will be assessed.

Vital signs data will be listed by participant including changes from baseline. The baseline for the vital signs' measurements will be the measurement obtained prior to administration of IV of XTMAB-16.

Table 7 Grading for Vital Signs

Vital Signs *	Mild (Grade 1)	Moderate(Grade 2)	Severe (Grade 3)	Potentially Life Threatening (Grade 4)
Fever (°C) ** (°F) **	38.0 – 38.4 100.4 – 101.1	38.5 – 38.9 101.2 – 102.0	39.0 – 40 102.1 – 104	> 40 > 104
Tachycardia - beats per minute	101 – 115	116 – 130	> 130	ER visit or hospitalization for arrhythmia
Bradycardia - beats per minute***	50 – 54	45 – 49	< 45	ER visit or hospitalization for arrhythmia
Hypertension (systolic) - mm Hg	141 – 150	151 – 155	> 155	ER visit or hospitalization for malignant hypertension
Hypertension (diastolic) - mm Hg	91 – 95	96 – 100	> 100	ER visit or hospitalization for malignant hypertension
Hypotension (systolic) – mm Hg	85 – 89	80 – 84	< 80	ER visit or hospitalization for hypotensive shock
Respiratory Rate – breaths per minute	17 – 20	21 – 25	> 25	Intubation

* Subject should be at rest for all vital sign measurements.

** Oral temperature; no recent hot or cold beverages or smoking.

*** When resting heart rate is between 60 – 100 beats per minute. Use clinical judgement when characterizing bradycardia among some healthy subject populations, for example, conditioned athletes.

Toxicity grading of vital signs will be summarized by dose cohort.

Descriptive statistics (n, mean, SD, median, minimum, maximum) for absolute values and changes from baseline will be presented by dose cohort.

ECG

Standard safety 12-lead ECGs will be performed as shown in the Schedule of Assessments.

The following ECG parameters will be recorded:

P wave, QRS complex, U wave, QRS duration, QT interval, QTcF, T wave, ST segment, RR interval, PR interval, and qualitative results.

The ECG will be evaluated by the Investigator as 'Normal', 'Abnormal, NCS' or 'Abnormal, CS'.

All ECG parameters will be listed by participant for each dose cohort and time point including changes from baseline. The baseline for the ECG measurements will be obtained prior to administration of IV of XTMAB-16.

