- d At each visit, participants will have a temperature check and will be asked if they have had exposure to someone known to have COVID-19. If the temperature is above 100°F (37.7°C) or the answer is "yes," participants will be tested for COVID-19. Participants who receive a COVID-19 vaccine prior to study entry must receive the final vaccine at least 30 days before dosing and will be tested for COVID-19 as per the SoA. Participants who wish to receive the COVID-19 vaccine after dosing must wait until after Week 4 PK sampling and other assessments have been completed. COVID-19 vaccination and any adverse reaction to the vaccine must be reported.
- e This will include a blood draw to test for blood alcohol levels.
- f From check-in at Day -2 to discharge from the unit on Day 8. Since the participants will be immunocompromised by administration of study treatment, the participants should be instructed to quarantine at home for 6 days after discharge from the clinical research unit.
- g When a meal, vital signs, ECG, or blood sample collection are scheduled at the same time as the study drug administration, the following order will be respected: ECG, vital signs, clinical biomarkers, PK, ADA, safety laboratory samples, and meal. To respect exact timing of PK samples (see Table 8), the other measurements will be done ahead of the scheduled time. The assessment schedule should be adapted to the design of the study.
- h During infusion, blood pressure and heart rate should be collected every 15 minutes for the first hour, every 30 minutes for the second hour, and hourly for 2 hours after the completion of infusion.
- i Blood samples will be collected for XTMAB-16 PK analysis at predose (Hour 0), at 1 hour after the start of infusion, 1 hour after the start of infusion, immediately after the 2-hour infusion (T; infusion termination), and at 3, 8, 14 hours on Day 1, and at 24 hours (Day 2), 50 hours (Day 3), 74 hours (Day 4), 170 hours (Week 2, Day 8), 338 hours (Week 3, Day 15), 674 (Week 4, Day 29), 1010 (Week 6, Day 43), 1346 hours (Week 8, Day 57), and 1682 hours (Week 10, Day 71) postinfusion of XTMAB-16 or placebo. All sampling time points after time T refer to time from the start of infusion. Acceptable windows for PK sample collection are provided in Table 8. The exact time of sample collection must be recorded on the eCRF.
- j Blood samples will be collected to evaluate biomarker concentrations of ACE, sIL-2R, IL-6, and sTNF α .

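### Fever and respiratory rate can end the infusion under Protocol 4.1.2.1, but only one scheduled in-infusion reading of each, at hour 1, clearly leaves time to act

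*Protocol*

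**What the plan says.** **The stop rule.** Protocol 4.1.2.1 covers participants in whom "vital signs changes of Grade 3 or 4 during infusion should have infusion terminated". Grading is by Appendix 4. Grade 1 or 2 changes are left to the Investigator's discretion. Anaphylaxis ends the infusion under a separate sentence.

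**What is graded.** Table 10 in Appendix 4 has seven rows: fever, tachycardia, bradycardia, systolic hypertension, diastolic hypertension, systolic hypotension, and "Respiratory Rate – breaths per minute". Grade 3 starts at 39.0 °C for fever and above 25 per minute for respiratory rate. The fever row carries a footnote specifying oral temperature.

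**What counts as a vital sign.** Protocol 8.2.3 states: "Oral, tympanic or temporal body temperature, respiratory rate, pulse, and systolic and diastolic blood pressure will be assessed". It asks for one temperature method, used consistently, and adds: "Respiration rate will be taken concurrently with all ECGs".

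**What is scheduled.** Footnote h in Protocol 1.3 sets the only intensified in-infusion frequency: "During infusion, blood pressure and heart rate should be collected every 15 minutes for the first hour, every 30 minutes for the second hour", then hourly for 2 hours afterwards. It names no other sign. SAP 6.1 repeats it: "During infusion, blood pressure and heart rate should be collected every 15 minutes for the first hour". Everything else follows the Table 1 columns, which around the infusion are hours 0, 1, 2 (T) and 3.

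**The concern.** The rule and the monitoring that feeds it do not match. Five of the seven Table 10 rows are heart-rate or blood-pressure rows and are read at 15 to 30 minute intervals. The other two, fever and respiratory rate, can end the infusion on the same terms but have no in-infusion frequency of their own.

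This is the first human exposure to a chimeric antibody, and 4.1.2.1 is the protocol's rule for stopping the infusion in an individual participant. As context, the Amendment 1 log says the acetaminophen pretreatment was removed and that participants would be closely monitored instead. Acetaminophen lowers fever, so fever is a sign for which monitoring now stands in for prophylaxis. At stake is how much drug runs in after a Grade 3 change in temperature or respiratory rate that has not shown itself clinically.

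**Working it through.** Neither document states a number of in-infusion readings, so there is no planned figure to reproduce. The counts follow from the schedule.

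**Inputs**
- Infusion: 120 minutes, uninterrupted (Protocol 1.1; section 6.1.2 says not less than 2 hours). A constant rate is assumed.
- Blood pressure and heart rate (footnote h): minutes 15, 30, 45, 60, 90, 120.
- Temperature and respiratory rate (Table 1): minutes 60 and 120. The SAP's copy of the table marks vital signs at every column. Footnote k puts ECGs at all time points, so tying respiratory rate to the ECGs gives the same hours.
- Timing of the T set: footnote g places other measurements ahead of the PK sample. Section 8.2.4 starts telemetry extraction, where applicable, at least 15 minutes before the nominal PK time. I therefore show a range, with T at minute 120 or (assumed) at minute 105.

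**Step 1: counts and gaps at nominal times**
- Blood pressure and heart rate: 6 readings, 5 before the end, longest gap 30 minutes.
- Temperature and respiratory rate: 2 readings, 1 before the end, longest gap 60 minutes.
- With T at minute 105, the first gap (0 to 60) is still 60 minutes. If the hour 1 set also moves to minute 45, the gap between the two sets is 105 − 45 = 60 minutes.

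**Step 2: dose that a stop can still spare**
- Stop at minute 60: 60/120 = 50% of the dose, or 2.0 mg/kg in the 4 mg/kg cohort.
- Stop at minute 105: 15/120 = 12.5%, or 0.5 mg/kg.
- Stop at minute 120: nothing.

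**Step 3: share of episodes met by a scheduled reading while drug is running**

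Assume onset is uniform over 0 to 120 minutes and the episode lasts D minutes. A reading at minute r meets every onset in the interval (r − D, r]. The share is the total length covered by these intervals within 0 to 120, divided by 120.

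- Temperature and respiratory rate, reading at 60 only: 15/120, 30/120, 60/120 for D = 15, 30, 60. Readings at 60 and 105: 30/120, 60/120, 105/120.
- Blood pressure and heart rate, readings at 15, 30, 45, 60, 90: 75/120, 90/120, 90/120. With 105 added: 90/120, 105/120, 105/120.
- Temperature and respiratory rate every 30 minutes, readings at 30, 60, 90: 45/120, 90/120, 90/120. With 105 added: 60/120, 105/120, 105/120.

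| Assumed episode length | Temp/resp. rate, as planned | BP/heart rate, as planned | Temp/resp. rate, every 30 min |
|---|---|---|---|
| 15 min | 12.5–25% | 62.5–75% | 37.5–50% |
| 30 min | 25–50% | 75–87.5% | 75–87.5% |
| 60 min | 50–87.5% | 75–87.5% | 75–87.5% |

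The lower figure has T at minute 120 and the upper has T at minute 105. The contrast is clear for shorter episodes. For 60-minute episodes it disappears if T is taken at minute 105.

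**The case against.** The strongest reply is that scheduled readings are not the only safeguard, and this largely stands. Section 6.5.1 asks for qualified staff and medication at all infusions. Footnote h itself brings staff to the bedside five times before the end. Additional ECGs, each with a respiratory rate, are at the Investigator's discretion. The anaphylaxis stop uses the Table 12 criteria, which include respiratory compromise and need no counted rate. That stop requires accompanying features, so it does not cover an isolated rate above 25. Telemetry is described as ECG data, and the footnote d temperature check is per visit; neither adds an in-infusion reading of these two signs.

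A second reply is that the Administration Guide and Pharmacy Manual, which are not available here, may already schedule these readings. That is possible. If they do, the change only brings the protocol into line.

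A reader might infer more than the documents support:
- **That termination is mandatory.** Section 4.1.2.1 uses *should* for Grade 3 or 4 vital signs and *will* for anaphylaxis. It is a directive, but the weaker of the two.
- **That participants receive 1.0 mg/kg of avoidable drug on average.** At 4 mg/kg, a mean wait of 30 minutes to the next nominal reading gives 4 × 30/120 = 1.0 mg/kg. This applies only to a persistent change that nobody notices before a scheduled reading.
- **That a reported result is affected.** SAP 4.11.4 says "Toxicity grading of vital signs will be summarized by dose cohort". It plans no separate during-infusion summary, so a misleading in-infusion zero is not a planned output.

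**Conclusion.** The mismatch is real and modest. Two of the seven graded rows that can end the infusion have one scheduled reading, at hour 1, that clearly leaves time to act, and a longest scheduled gap of up to 60 minutes against 30 for the other five. A T set taken up to 15 minutes early adds a second usable reading, but a stop at that point spares at most 12.5% of the dose.

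The counts and gaps rest only on the schedule and an uninterrupted 2-hour infusion. The capture shares also rest on uniform onset, assumed episode lengths and the assumed T timing. The practical exposure is a Grade 3 fever or respiratory rate that is not noticed clinically. The documents do not show that participants are unobserved during infusion, and they set no 30-minute standard for these signs; that interval is simply the longest gap the plan accepts for blood pressure and heart rate. This is a cheap safety improvement. PK and the planned analyses are unaffected.

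**What to change.** In footnote h of Protocol 1.3 and its copy in SAP 6.1, add temperature and respiratory rate at least every 30 minutes until the infusion ends, taken with the blood-pressure and heart-rate readings already scheduled. Use the single temperature method chosen for the study under 8.2.3. Oral matches the Table 10 footnote; if tympanic or temporal is chosen, state how the Table 10 fever grades apply to it.

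For a 2-hour infusion the cost is two extra sets per participant, at minutes 30 and 90: 2 × 24 = 48 in total, all at existing bedside contacts. A longer infusion would add more. Under 8.2.3 a respiratory rate is a 30-second count, and an oral temperature needs 5 minutes without food or liquid. Section 4.1.2.1, the sample size, PK sampling and the SAP methods need no change.

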- k Single 12-Lead ECGs will be collected at all time points. Additional ECGs will be performed at the discretion of the Investigator. Telemetry recording will begin on Day -1 and continue through 50 hours after the start of infusion. At specified time points, for extraction of telemetry data, participants should be in a semi-reclined resting position for at least 10 minutes prior to the target time of data extraction (at least 15 minutes when coinciding with PK/ADA/nAb blood collection). On Day -1, resting periods for telemetry data extraction should occur at 1, 2, 3, and 8 hours (corresponding to the projected time points on Day 1). On Day 1, resting periods for telemetry data extraction should occur at predose (to match the time point for 24 hours after the start of infusion) and 1, 2, 3, 8, and 24 hours after the start of infusion. A resting period for telemetry data extraction will also occur at 50 hours after the end of infusion. During infusion, data will be collected in a semi-supine/semi-reclined position, and for all other readings, data will be collected in a supine position.
- l Tryptase levels will be assessed at Baseline for all participants. For any participant who experiences anaphylaxis within 4 hours after the end of infusion, and additional sample for assessment of tryptase levels should be collected as soon as is reasonable. See [Appendix 5](#) for diagnosis and treatment of anaphylaxis.

- m Blood samples for PK/ADA/nAb will be collected for analysis from participants who experience an SAE that is also considered related to study treatment.

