#### 8.2.4 ELECTROCARDIOGRAMS

Participants will undergo telemetry beginning on Day -1 through 50 hours after the start of infusion ([Table 8](#)). Five-minute telemetry data extraction periods should begin after 10 minutes of rest in a semi-reclined position, and when applicable, at least 15 minutes prior to the nominal PK/ADA/nAb blood collection time point and to allow completion of the ECGs prior to collection of PK/ADA/nAb sample.

Standard 12-lead ECGs will be recorded after the participant has been resting at least 10 minutes using a CAM-14 module. Single ECGs will be collected at the time points noted in the SoA (Section [1.3](#)). Additional ECGs will be performed at the discretion of the Investigator.

Telemetry and ECG readings will be performed in a supine position after the allotted time specified above. During the infusion, procedures will be performed in a semi-supine/semi-reclined position.

The Investigator will be responsible for reviewing the ECG to assess whether the ECG is within the reference limits and to determine clinical significance of the results. If necessary, the Investigator has the right to override the interpretation and intervals as measured by the ECG machine. The ECG will be assessed for the following measures: P wave, QRS complex, U wave, QRS duration, QT interval, QTcF, T wave, ST segment, RR interval, PR interval, and qualitative results.

---

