#### 9.4.1 GENERAL APPROACH

Details of the data analysis for this study will be provided in the Statistical Analysis Plan (SAP), which will be finalized prior to database lock.

Unless otherwise specified, the last value obtained prior to infusion of study medication (Day 1) will be used as the baseline value. If a baseline measurement is missing, and a screening value available, the screening value will be utilized as Baseline instead.

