3.2.4 Safety Variables

- Vital signs (supine blood pressure [BP] and pulse, tympanic (ear), oral and temporal body temperature, respiratory rate)
- 12-lead electrocardiograms (ECG): P wave, QRS complex, U wave, QRS duration, QT interval, QTcF, T wave, ST segment, RR interval, PR interval, and qualitative results.
- Telemetry
- Clinical laboratory tests (hematology, biochemistry, urinalysis, Virology, Urine Drug abuse Screening, Serum Pregnancy Test)
- Adverse event (AE) assessments
- Physical examinations

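### Two positions are prescribed for the same telemetry extractions, and ECG and vital-sign changes during infusion set a semi-supine reading against a supine baseline

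*Protocol*

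**What the plan says.** **Telemetry.** Protocol Table 1, footnote k, says that at the specified extraction points "participants should be in a semi-reclined resting position for at least 10 minutes prior to the target time of data extraction". Those points are 1, 2, 3 and 8 h on Day -1, and predose, 1, 2, 3, 8, 24 and 50 h from Day 1. The footnote then closes with the general rule "During infusion, data will be collected in a semi-supine/semi-reclined position, and for all other readings, data will be collected in a supine position". Protocol 8.2.4 has the same pair of instructions: "Five-minute telemetry data extraction periods should begin after 10 minutes of rest in a semi-reclined position", and then "Telemetry and ECG readings will be performed in a supine position after the allotted time specified above", with semi-supine only for procedures during the infusion. SAP 6.1 reproduces footnote k unchanged.

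**12-lead ECG.** The general rule above applies: semi-supine during infusion, supine otherwise.

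**Vital signs.** Protocol 8.2.3 has blood pressure and pulse semi-reclined during the infusion, then: "For all other readings, blood pressure and pulse will be taken in a supine position after 10 to 15 minutes rest". SAP 3.2.4 lists the variable only as "supine blood pressure [BP] and pulse".

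**Baseline.** Protocol 9.4.1: "the last value obtained prior to infusion of study medication (Day 1) will be used as the baseline value". SAP 4.2 likewise takes the last value before dosing, unscheduled readings included.

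**Use.** Changes from baseline in ECG and vital signs, and the time-matched digital ECG, are endpoints (Protocol 3; primary in SAP 3.2.1). SAP 4.11.4 tabulates ECG changes by dose cohort and pooled placebo, counts QTcF increases above 30 and 60 ms, and allows an optional concentration-QT model. Neither document mentions posture as a factor in any analysis.

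**The concern.** A change from baseline can be read as a treatment effect only if nothing else differs systematically between the two readings. Here posture can differ at the time points that fall in the infusion, and it differs in the same direction for every participant.

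For telemetry, the purpose of the Day -1 recording is to hold everything but treatment constant at a given clock time. Staff following footnote k cannot tell whether the Day -1 readings at 1 and 2 h should be supine or semi-reclined. If practice varies between participants or cohorts, the data will not show which was used, because neither document asks for posture to be recorded.

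For 12-lead ECG and vital signs there is no ambiguity: the positions differ by design. At stake is the reading of the in-infusion change tables and the categorical QTcF change counts in a first-in-human study. No hypothesis test depends on it (Protocol 9.1).

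**Working it through.** The plan states no figure that depends on posture, so there is nothing to reproduce. The check sets the position rules side by side, pair by pair, and then follows a shift through the planned summaries.

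**1. Telemetry pairs.** A 2-hour infusion is assumed.

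| Baseline reading | Day 1-2 reading | Supine rule outside infusion | Semi-reclined throughout |
|---|---|---|---|
| Day -1, 1 h | 1 h | supine vs semi-supine: differ | match |
| Day -1, 2 h | 2 h | supine vs semi-supine: differ | match |
| Day -1, 3 h | 3 h | match | match |
| Day -1, 8 h | 8 h | match | match |
| Day 1 predose | 24 h | match | match |

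So 2 of 5 pairs differ under one instruction and 0 of 5 under the other. A third literal reading of 8.2.4, resting semi-reclined and then moving to supine for the reading, gives the same mismatch as the first.

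**2. Where the 2 h reading falls.** Footnote i puts the PK sample immediately after the infusion. Footnote g has the other measurements done ahead of the PK time. Section 8.2.4 starts the extraction at least 15 minutes before that sample, that is, at or before 120 - 15 = 105 minutes. The 2 h telemetry reading is therefore inside the infusion, and the 2 h ECG and vital signs probably are too.

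**3. 12-lead ECG and vital signs.** The predose reading is not taken during infusion, so it is supine, and it is the baseline. The 1 h reading, and probably the 2 h reading, is semi-supine.

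**4. Effect on summaries.** Let d be the mean posture shift and e the drug effect at a given time.
- Within-arm mean change, active: e + d.
- Within-arm mean change, placebo: d.
- Same-time contrast: (e + d) - d = e. The shift cancels in expectation, with 9 + 9 = 18 active and 3 + 3 = 6 placebo participants.
- Categorical counts: P(change > 30 ms) = 1 - Phi((30 - d)/SD), taking e = 0.

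The documents give neither d nor the SD. The values below are assumptions, and d could have either sign.

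| Assumed SD | d = -5 ms | d = 0 | d = +5 ms | d = +10 ms |
|---|---|---|---|---|
| 10 ms | 0.02% | 0.1% | 0.6% | 2.3% |
| 15 ms | 1.0% | 2.3% | 4.8% | 9.1% |

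Example: SD 15, d = +5 gives (30 - 5)/15 = 1.67 and an upper tail of 4.8%.

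**5. Concentration-QT model.** SAP 4.11.4 specifies concentration, treatment and a random participant intercept. A shift at 1 and 2 h in all arms is a function of time alone. With no time term, it is shared among the intercept, treatment and concentration terms. This was illustrated with simulated data: 18 active and 6 placebo; Cmax 47.8 and 95.7 and AUC 28000 from Protocol Table 3; assumed variability; two decline shapes; three sets of sampling times; one data set per combination. An assumed +5 ms shift moved the predicted placebo-corrected change at Cmax by -2.1 to +0.9 ms. With nominal time as a factor the movement was 0.0 ms, as it must be: an indicator for 1 and 2 h is a sum of time-point indicators.

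**The case against.** **The telemetry pairs may well match.** If the semi-reclined instruction governs, all five do. This stands. A reader might infer that the time-matched baseline is broken. The documents support only that two instructions conflict and that one of them mismatches two pairs. The Amendment 2 log describes the posture rule as supine at all times outside infusion, which leans towards the mismatching reading. It does not settle the matter, because the semi-reclined instruction remains in the current text.

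**The affected readings are not uniquely those near peak concentration.** This stands. At 1 h of a constant-rate 2-hour infusion the concentration is about half its peak. With the mouse half-lives of 226.9 to 327.2 h in Protocol 4.2, and ignoring distribution, the fall from 2 to 3 h is 1 - 2^(-1/226.9) = 0.3% down to 1 - 2^(-1/327.2) = 0.2%. The 3 h pair is matched in posture and lies almost at the peak.

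**An assumed shift should not be set against the 10 ms limit in SAP 4.11.4.** This also stands. The limit applies to the upper 90% confidence bound of a placebo-corrected estimate, in an analysis done only if telemetry raises findings. A within-arm shift is a different quantity.

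**Safety grading is untouched.** Vital-sign grades use absolute values (Protocol Table 10; SAP Table 7), so baseline posture does not enter them. SAP 4.2 pools placebo for safety summaries, so a common shift would show in that column. This limits the harm to interpretation. The vital-sign text in SAP 4.11.4, however, says only by dose cohort and does not name the placebo column.

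**The infusion posture was deliberate.** The amendment log ties it to site practice and an IRB letter. Nothing here asks for it to change.

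**SAP 3.2.4 is only a label.** That is so: SAP 4.11.4 states no posture and SAP 6.1 carries footnote k. It is still wrong for the in-infusion readings.

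**Conclusion.** The concern holds in limited form. For telemetry, footnote k and Protocol 8.2.4 contradict themselves. If the supine rule is followed, the 1 and 2 h pairs of a listed endpoint carry a posture shift; the other three pairs do not under either rule. For 12-lead ECG and vital signs, the change from baseline at 1 h, and probably 2 h, mixes posture with treatment by design.

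The shift stays in the within-arm change tables and in the counts of QTcF increases above 30 and 60 ms, and the optional concentration-QT model does not absorb it. It cancels in expectation in a same-time placebo contrast, though that contrast rests on 6 placebo participants. The documents give no size for the shift, so every millisecond figure above is illustrative. The finding rests on the position rules, a 2-hour infusion, and ECG and vital signs being taken before the PK sample at 2 h. The documents do not show that the time-matched comparison fails as a whole, or that a QT conclusion would be overturned.

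**What to change.** 1. **Telemetry.** In footnote k, its copy in SAP 6.1, and Protocol 8.2.4, prescribe one position for both members of each time-matched pair. The semi-reclined position already named does this and fits the infusion. Delete supine for telemetry extractions. Cost: wording only, with no extra reading.

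2. **12-lead ECG and vital signs.** Keep the last pre-infusion supine value as baseline for supine readings after the infusion. Do not substitute Day -2: that would give 12 of the 14 scheduled post-dose ECG times an older baseline in order to repair two. For the in-infusion readings, choose one of the following.
   - Add a semi-supine predose ECG and vital-sign set as their baseline only. Cost: one short extra set per participant and a second baseline flag. SAP 4.2 must then name which set serves which readings. Otherwise a semi-supine set taken last before dosing would become the baseline for everything.
   - Footnote the posture difference in the in-infusion change tables and interpret them against pooled placebo at the same time point, naming the pooled placebo column for vital signs in SAP 4.11.4. Cost: wording only. The within-arm changes and the categorical counts still contain the shift.

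3. **Concentration-QT model.** Add nominal time as a factor in SAP 4.11.4. Cost: one model term.

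4. **SAP 3.2.4.** Replace the supine label with the two positions actually used.
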